# 9.4.1.8 Time from randomization to second progression

PFS2 will be defined as the time from the date of randomization to the earliest of the progression event subsequent to first subsequent therapy or death. The date of second progression will be recorded by the Investigator in the eCRF at each assessment and defined according to local standard clinical practice and may involve any of the following: objective radiological imaging, symptomatic progression, or death. Patients alive and for whom a second disease progression has not been observed should be censored at the last time known to be alive and without a second disease progression, that is, censored at the latest of the PFS or PFS2 assessment date if the patient has not had a second progression or death.

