3.2.1 Progression-free survival (PFS)

PFS (per RECIST 1.1 as assessed by the BICR) will be defined as the time from the date of randomization until the date of objective disease progression or death (by any cause in the absence of progression) regardless of whether the patient withdraws from randomized therapy or receives another anti-cancer therapy prior to progression (i.e. date of event or censoring – date of randomization + 1). Patients who have not progressed or died at the time of analysis will be censored at the time of the latest date of assessment from their last RECIST 1.1 assessment. However, if the patient progresses or dies after 2 or more consecutive missed visits, the patient will be censored at the time of the latest RECIST 1.1 assessment prior to the 2 missed visits (Note: NE is not considered a missed visit). A 'look-back' approach will be taken (i.e. if an event e.g. progression or death is observed, then it will be considered an event only if there is an assessment within the 2 visit window immediately before the event, irrespective of whether there were missed visits prior to that assessment). If the patient has no evaluable visits or does not have baseline data they will be censored at Day 1 unless they die within 2 visits of baseline i.e. ≤ 119 days (2 x 8 weeks plus 1 week allowing for a late assessment within the visit window), then they will be treated as an event with date of death as the event date.

Given the scheduled visit assessment scheme (i.e. $q8w \pm 1w$ for the first 72 weeks then $q12w \pm 1w$ up to 96 weeks then $q24w \pm 1w$ thereafter) the definition of 2 missed visits will change. See Appendix B for further details on the derivation of the 2 missed visit rule for RECIST assessments.

The PFS time will always be derived based on scan/assessment dates not visit dates.

PFS will also be obtained using the algorithm described above for the RECIST site investigator tumor data.

RECIST 1.1 assessments/scans contributing towards a particular visit may be performed on different dates. The following rules will be applied:

- For BICR assessments, the date of progression will be determined based on the earliest scan dates of the component that triggered the progression for the adjudicated reviewer selecting PD or of the reviewer who read baseline first if there is no adjudication.

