3.2.2 Overall survival (OS)

Overall survival is defined as the time from the date of randomization until death due to any cause (i.e. date of death or censoring – date of randomization + 1). Any patient not known to have died at the time of analysis will be censored based on the last recorded date on which the patient was known to be alive (see Appendix C).

Note: Survival calls will be made in the week following the date of Data Cut Off (DCO) for the analysis (these contacts should generally occur within 7 days of the DCO). If patients are confirmed to be alive or if the death date is post the DCO date, these patients will be censored at the date of DCO. The status of ongoing, withdrawn (from the study) and "lost to follow-up" patients at the time of the final OS analysis should be obtained by the site personnel by checking the patient's notes, hospital records, contacting the patient's general practitioner and checking publicly-available death registries. In the event that the patient has actively withdrawn consent to the processing of their personal data, the vital status of the patient can be obtained by site personnel from publicly available resources where it is possible to do so under applicable local laws.

Note, for any OS analysis performed prior to the final OS analysis, in the absence of survival calls being made, it may be necessary to use all relevant CRF fields to determine the last recorded date on which the patient was known to be alive for those patients still on treatment (since the SURVIVE module is only completed for patients off treatment if a survival sweep is not performed). The last date for each individual patient is defined as the latest among the dates recorded on the case report forms (CRFs) (see Appendix C).

If any of the dates from the CRFs are after study discontinuation or after the DCO, then the minimum of the study discontinuation and DCO date will be used instead.

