3.2.6 Time to death or distant metastasis (TTDM)

TTDM (per RECIST 1.1 as assessed by BICR) will be defined as the time from the date of randomization until the first date of distant metastasis or death in the absence of distant metastasis. Distant metastasis is defined as any new lesion that is outside of the radiation field according to RECIST 1.1 or proven by biopsy. For this reason, the TTDM endpoint will be determined from recurrent disease that occurs outside of the structures contained within the thorax, including lymph nodes, pulmonary, pleural, and mediastinal metastatic sites and excluding the heart. The locations of distant metastases will be defined and documented prior to database lock/unblinding.

Patients who have not developed distant metastasis or died at the time of analysis will be censored at the time of the latest date of assessment from their last RECIST 1.1 assessment. However, if the patient has distant metastasis or dies after 2 or more consecutive missed visits, the patient will be censored at the time of the latest evaluable RECIST 1.1 assessment prior to the 2 missed visits. If the patient has no evaluable visits or does not have baseline data they will be censored at Day 1 unless they die within 2 visits of baseline.

A sensitivity analysis of TTDM may be performed using Investigator assessments according to RECIST 1.1.

3.2.7 Proportion of patients alive at 24 months and 36 months after randomization (OS24 and OS36)

The OS24 and OS36 will be defined as the Kaplan-Meier estimate of OS at 24 months and 36 months after randomization, respectively.

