3.2.8 Time from randomization to second progression or death (PFS2)

PFS2 will be defined as the time from the date of randomization to the earliest of the progression event subsequent to the first subsequent anticancer therapy (excluding radiotherapy) or death (i.e. date of PFS2 event or censoring – date of randomization + 1). The date of second progression will be recorded by the investigator in the eCRF at each assessment and defined according to local standard clinical practice and may involve any of

the following: objective radiological imaging, symptomatic progression or death. The date of the PFS2 assessment and investigator opinion of progression status (progressed or non-progressed) at each assessment will be recorded in the eCRF. Patients must have had a first progression event and received subsequent systemic anticancer therapy (excluding radiotherapy) for a second progression event to be valid. Second progression status will be reviewed every 8 weeks following the progression event used for the primary variable PFS (the first progression) and status recorded. Patients alive and for whom a second disease progression has not been observed should be censored at the earliest of: date of study termination, date last known alive, DCO, or if a patient has not had a first subsequent therapy; the date last known not to have received a first subsequent therapy (TFST censoring date).

However, if the patient experiences a second progression or dies after 2 or more consecutive missed visits, the patient will be censored at the time of the last PFS2 assessment prior to the 2 missed visits.

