APPENDIX B. 2 MISSED VISIT RULES

RECIST 1.1. Assessments

For RECIST 1.1 assessments, we will apply a 'look-back' approach to the 2 missed visit rule. That is, if an event (e.g. progression or death) is observed, then it will be considered an event only if there is an assessment within the 2 visit window immediately before the event, irrespective of whether there were missed visits prior to that assessment. If there are 2 consecutive missed visits prior to the event, the event will be censored as the last valid RECIST 1.1 assessment, prior to the 2 missed visits. For example:

Week 8	Week 16	Week 24	Week 32	Week 40	Censor for 2 missed visit rule?
Event?	Event?	Event?	Event?	Event?	_
No	Missed visit	Missed visit	No	Yes	No
No	No	Missed visit	Missed visit	Yes	Yes – censor at week 16

Given the scheduled visit assessment for RECIST (i.e. $q8w \pm 1w$ for the first 72 weeks then $q12w \pm 1w$ up to 96 weeks then $q24w \pm 1w$ thereafter) the definition of 2 missed visits window will change:

Length of 2 missed visit window for RECIST assessments

Missing baseline or within 2 visits of baseline:

- A patient without baseline will be censored at day 1 unless they die ≤ day 119 (week 17).
- Any scan ≤ day 119 (week 17) is within 2 visits of baseline and therefore cannot be censored for missing visits.

Schedule: q8w:

 For any scan > day 119 until ≤ day 511 (week 73) the visit schedule is q8w ±1 week and thus the maximum time between two consecutive scans is 1+8+8+1=18 weeks (126 days).

Schedule: change from q8w to q12w:

 For any scan > day 511 until ≤ day 595 (week 85) the visit schedule is q12w ±1 week and the visit schedule for the cycle before was q8w ±1 week and thus the maximum time between two consecutive scans is 1+8+12+1=22 weeks (154 days).

Schedule: q12w:

 For any scan > day 595 until ≤ day 679 (week 97) the visit schedule is q12w ±1 week and the visit schedule for the cycle before was q12w ±1 week thus the maximum time between two consecutive scans is 1+12+12+1=26 weeks (182 days).

[figure not shown]
Schedule: change from q12w to q24w:

[figure not shown]
 For any scan > day 679 until ≤ day 847 (week 121) the visit schedule is q24w ±1 week and the visit schedule for the cycle before was q12w ±1 week and thus the maximum time between two consecutive scans is 1+12+24+1=38 weeks (266 days).

[figure not shown]
Schedule: q24w:

[figure not shown]

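### The SAP's PFS2 censoring date depends on outcome after a gap in assessment, departs from the protocol definition without saying so, and pushes Kaplan-Meier PFS2 upward

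*SAP*

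**What the plan says.** SAP 3.2.8 has two rules for a patient who has started subsequent therapy.

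- **Alive, no second progression recorded:** such patients "should be censored at the earliest of: date of study termination, date last known alive, DCO". Only patients without subsequent therapy get an earlier date, the TFST censoring date.
- **Second progression or death after at least two consecutive missed visits:** "the patient will be censored at the time of the last PFS2 assessment prior to the 2 missed visits".

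On the schedule, the same section states: "Second progression status will be reviewed every 8 weeks following the progression event used for the primary variable PFS".

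Protocol 9.4.1.8 counts second progression or any death as the event and has no missed-visit exclusion. It asks for the last time a patient was known to be both alive and free of second progression, and spells this out as "censored at the latest of the PFS or PFS2 assessment date if the patient has not had a second progression or death".

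The SAP treats its other assessment-based endpoints differently. An event-free patient for PFS (SAP 3.2.1) "will be censored at the time of the latest date of assessment from their last RECIST 1.1 assessment". TTDM (SAP 3.2.6) follows the same principle for its event-free group: "not developed distant metastasis or died at the time of analysis will be censored at the time of the latest date of assessment". SAP Section 6 lists four changes from the protocol, and none concerns PFS2. Appendix B has a part headed "Length of 2 missed visit window for RECIST assessments" and matching parts for QLQ-LC13 and QLQ-C30, but nothing for PFS2.

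**The concern.** Two patients with the same gap in PFS2 assessment get different censoring dates according to what happened to them. The survivor stays in the risk set through the gap, often to data cut-off. SAP 3.2.2 shows how the last-alive date behaves: for patients confirmed alive by the survival calls, "these patients will be censored at the date of DCO". The patient who progressed again or died leaves the risk set at the start of the gap and the event disappears, even when it is a documented death.

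Both rules raise the Kaplan-Meier curve. PFS2 is a secondary endpoint reported with a stratified log-rank test, hazard ratio, medians and curves, so the reported level of PFS2 would be too favourable in both arms. If gaps were more common in one arm, the hazard ratio would shift too, in either direction.

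The missed-visit rule is also not fully specified. It has no window or starting point for PFS2. PFS2 review begins only after first progression, so a patient who dies before then has no PFS2 assessment to be censored at.

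**Working it through.** The documents give no event count, median or power for PFS2, so there is no planned figure to reproduce.

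**Step 1: who is affected.** Patients on subsequent therapy whose PFS2 assessment lapses for at least two visits while survival is still followed. Patients without subsequent therapy (TFST date) and events after a single missed visit are not affected.

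**Step 2: direction.** The estimate is S(t) = Π(1 − d/n) over event times, with d events among n at risk. Take ten patients on subsequent therapy who all stop PFS2 visits at month 12. Six die at month 20 and four are alive at data cut-off, month 36.

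- Counting known deaths with all ten at risk: S(36) = 1 − 6/10 = 0.40.
- SAP: six censored at 12, four at 36, no events, so S(36) = 1.00.
- Protocol 9.4.1.8 taken literally: the four survivors leave at month 12 and the six deaths count, so S = 1 − 6/6 = 0.

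This extreme case shows direction only. It also shows that the protocol rule can err the other way.

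**Step 3: illustrative size.** Simulation of 300,000 patients per arm.

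- From the documents: PFS medians 10 and 15.4 months (10 + 5.4) and 38-month accrual (SAP 1.3); 8-weekly PFS2 review (SAP 3.2.8).
- Assumed: exponential PFS with 10% of events deaths; subsequent therapy 1 month after first progression; second progression at median 5 (placebo) or 6 (durvalumab) months after therapy starts; death before second progression at median 20 months from first progression, and after it at median 8 months; PFS2 assessment stopping at 10% or 20% per year from therapy start with survival follow-up intact; data cut-off at 65 months.

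About 3.6% or 7.2% of the durvalumab arm then has a gap of two or more visits: 0.036 × 262 ≈ 9 patients, or 0.072 × 262 ≈ 19.

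Durvalumab 36-month PFS2, true value 0.289:

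| Rule | 10% stopping | Error | 20% stopping | Error |
|---|---|---|---|---|
| SAP 3.2.8 | 0.303 | +0.014 | 0.318 | +0.029 |
| Assessment-date censoring, missed-visit rule kept | 0.299 | +0.010 | 0.311 | +0.022 |
| SAP censoring date, missed-visit rule dropped | 0.297 | +0.008 | 0.305 | +0.016 |
| Protocol 9.4.1.8 | 0.293 | +0.004 | 0.299 | +0.010 |

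Changing only the censoring date removes 0.004 or 0.007 of the excess. Dropping only the missed-visit rule removes 0.006 or 0.013. At 20% stopping the durvalumab median is 23.3 months true, 24.3 under the SAP and 24.0 under the protocol.

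**Step 4: sensitivity.** Varying the data cut-off (50 to 74 months), survival before and after second progression, and time to second progression gives a SAP excess at 36 months of 0.009 to 0.058 and a protocol-rule error of −0.001 to +0.028. At 5% stopping the SAP excess is about 0.006 to 0.009. With no gaps the protocol rule is 0.001 to 0.004 too low.

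A separate simulation used other assumptions: one arm with median PFS 10 months, 5% to 30% of treated patients stopping visits, and a 126-day window. The true value was about 0.204. The SAP was too high in every scenario, by 0.003 to 0.034. The protocol rule gave 0.199 to 0.211.

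**Step 5: hazard ratio** (true 0.637).

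| Stopping per year, placebo / durvalumab | SAP | Protocol |
|---|---|---|
| 20% / 20% | 0.638 | – |
| 10% / 20% | 0.614 | 0.629 |
| 20% / 10% | 0.662 | 0.647 |

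**The case against.** **The outcome-dependent date is the smaller cause.** This stands. At 10% or 20% stopping, making the date symmetric while keeping the missed-visit rule removes about a quarter of the excess (0.004 of 0.014, or 0.007 of 0.029). The missed-visit rule does more, and that rule is also absent from the protocol's PFS2 definition.

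**Real gaps may be less damaging than assumed.** This stands in part. Protocol Table 2 schedules second-progression review every 8 weeks and has scan readings collected from medical charts after progression. Patients who leave the study are censored no later than study termination. If second progressions during gaps are recovered from charts, the SAP excess falls to between 0.003 and 0.014, roughly half, but remains upward.

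**The protocol rule is not unbiased.** This also stands. It counts late events at their actual dates while event-free patients stop at the last assessment. With chart recovery it was 0.002 to 0.004 too low. The SAP date without the missed-visit rule then matched the true value to three decimals in one run, and at 5% stopping the full SAP rule (+0.003) was about as close as the protocol rule (−0.004). So the protocol rule is not always the closest.

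**The SAP may set missing-data rules, and PFS and TTDM use a missed-visit rule too.** Protocol 9.5 does leave missing-data handling to the SAP. But the protocol itself fixes the PFS2 censoring date, and PFS and TTDM do not carry event-free patients across the gap.

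**A death before first progression would naturally count as an event, because no PFS2 visit was due.** That is a reasonable reading, but SAP 3.2.8 does not state it.

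**Conclusion.** The concern holds. SAP 3.2.8 makes the censoring date after a gap of two or more visits depend on outcome, departs from protocol 9.4.1.8 in both of its rules without recording it in Section 6, and leaves the missed-visit window undefined for PFS2. The Kaplan-Meier estimate is biased upward.

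The size rests on assumed gap rates. At 10% to 20% stopping per year the base case puts 36-month PFS2 too high by 0.014 to 0.029. The excess is under 0.01 at 5% stopping, and roughly halves if second progressions in gaps are recovered from charts. The hazard ratio is essentially unchanged when gaps are equal between arms, and the documents give no reason to expect a difference in this double-blind trial. PFS2 lies outside the multiple testing procedure, so trial success is not affected. What is at stake is the accuracy of a reported secondary endpoint and its agreement with the protocol.

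**What to change.** In SAP 3.2.8:

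1. Censor living patients without a second progression at the latest PFS or PFS2 assessment date, as protocol 9.4.1.8 does. Keep the TFST censoring date for patients with no subsequent therapy.
2. Drop the missed-visit rule for PFS2. This does the most to remove the excess. If it is kept, give its window and starting point for PFS2 in Appendix B, state how a death before any PFS2 assessment is handled, and add a sensitivity analysis that counts events after gaps at their actual dates.
3. List any remaining difference from protocol 9.4.1.8 in SAP Section 6, including the TFST date.

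The cost is two sentences in 3.2.8, one entry in Section 6 and a small derivation change, with no new data collection. PFS2 medians may come out slightly less favourable. A small bias remains under the protocol rule: slightly low when gaps are rare or recovered from charts, and otherwise upward but smaller than under the SAP in the base case.

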3.2.9 Best objective response (BoR)

BoR is calculated based on the overall visit responses from each RECIST assessment. It is the best response a patient has had following randomization but prior to starting any subsequent anticancer therapy (excluding radiotherapy) and up to and including RECIST progression or the last assessment in the absence of RECIST progression and subsequent cancer therapy.

Categorization of BoR will be based on RECIST using the following response categories: CR, PR, SD, PD and NE.

For determination of a best response of SD, the earliest of the dates contributing towards a particular overall visit assessment will be used. SD should be recorded at least 8 weeks minus 1 week, i.e. at least 49 days (to allow for an early assessment within the assessment window), after randomization (i.e. study day 50). For CR/PR, the initial overall visit assessment which showed a response will use the latest of the dates contributing towards a particular overall visit assessment.

BoR will be determined programmatically based on RECIST from the overall visit response using all BICR data up until the first progression event, the start of subsequent cancer therapy or the last assessment in the absence of progression/subsequent cancer therapy. The denominator will be consistent with that used in the ORR analysis. In particular, patients with no evidence of disease will be excluded.

For patients whose PFS event is death, BoR will be calculated based upon all evaluable RECIST assessments prior to death.

For patients who die with no evaluable RECIST assessments, if the death occurs \leq 119 days (i.e. 2 x 8 weeks + 1 week to allow for a late assessment within the assessment window) after randomization, then BoR will be assigned to the progression (PD) category. For patients who die with no evaluable RECIST assessments, if the death occurs >119 days (i.e. 2 x 8 weeks + 1 week) after randomization then BoR will be assigned to the NE category.

A patient will be classified as a responder if the RECIST criteria for a CR or PR are satisfied at any time following randomization, prior to RECIST progression and prior to starting any subsequent cancer therapy.

3.2.10 Change in TL tumor size

For supportive purposes percentage change from baseline in tumor size will be derived at each scheduled tumor assessment visit (i.e. week 8, week 16 etc hereafter referred to as week X for convenience). Best percentage change from baseline in tumor size will also be derived as the biggest decrease or the smallest increase in tumor size from baseline.

This is based on RECIST target lesion measurements taken at baseline and at the timepoint of interest. Tumor size is defined as the sum of the longest diameters of the target lesions for the BICR data based upon RECIST assessments. Target lesions are measurable tumor lesions. Baseline for RECIST is defined to be the last assessment prior to randomization. The change in target lesion tumor size at week X will be obtained for each patient by taking the difference between the sum of the target lesions at week X and the sum of the target lesions at baseline. To obtain the percentage change in target lesion tumor size at week X the change in target lesion tumor size is divided by the sum of the target lesions at baseline and multiplied by 100 (i.e. (week X - baseline) / baseline * 100). More details on target lesions and measurements can be found in Section 3.1.

The above derivations will be programmed for the BICR data based upon RECIST assessments. Measurements from the reviewer selected by the adjudicator will be used when adjudication for overall visit response has occurred, but in the case where no adjudication was required the measurements from the reviewer who reviewed the baseline scan first will be used for this analysis.

